1. INTRODUCTION

1.1 Study Disease

Prostate cancer is very common with about 1 in 8 men being diagnosed with prostate cancer during their lifetime ¹. There are different treatment options for localized prostate cancer including surgery, external beam radiotherapy (EBRT), brachytherapy and hormonal systemic treatment or multimodality approaches ². More recently, high dose rate (HDR) brachytherapy techniques have been developed in addition to the low dose rate (LDR) brachytherapy permanent radioactive seed implants for prostate cancer treatment. HDR brachytherapy has become a standard of care option as monotherapy or in combination with EBRT plus/minus androgen deprivation therapy as a boost ^{3 4}. HDR brachytherapy has also been increasingly used to treat recurrent prostate cancer with local failures in the prostate after radiotherapy ^{5 6}.

1.2 Rationale

HDR brachytherapy in the treatment of prostate cancer is a procedure consisting of insertion of hollow needles into the prostate under transrectal ultrasound (TRUS) guidance with the patient in dorsal lithotomy position. An intraoperative radiation plan is created following acquisition of a planning image and delineation of the targets (prostate) and organs-at-risk (OARs including rectum, bladder, and urethra). The radiation plan is then delivered with an iridium-192 source using an afterloader machine. The needles are removed, and the patient is transferred to a recovery area followed by same day discharge.

A key component of radiotherapy planning, including HDR brachytherapy planning, is identifying the volumes that will be treated and OARs that will be spared to deliver a safe radiation treatment through contouring of structures. Contouring for HDR prostate brachytherapy can be done on TRUS, CT or MRI images ^{7 8}. TRUS is often preferred as it offers the convenience of the patient remaining in the same position throughout the entire procedure without a need to be moved for CT or MRI acquisition, which saves both time and resources. However, poor soft tissue contrast, prostate deformation and artifact on ultrasound can make prostate delineation on TRUS challenging especially with the needles in place for HDR treatment. The difficulty in contouring can be compounded for new learners developing brachytherapy expertise and working on obtaining proficiency in ultrasound-based prostate contouring.

With the advent of deep-learning artificial algorithms, auto-contouring has been continually integrated into routine clinical use in EBRT planning. Deep learning algorithms are being developed for brachytherapy planning and can be a useful tool for learning brachytherapy contouring during the implant procedure. The standard U-net algorithm being investigated in this study was assessed retrospectively in a pilot cohort of 150 patients (110 training, 20 validation and 20 testing sets) to estimate the geometric accuracy of the algorithm ⁹. This was the first study to investigate auto-contouring with the needles in place in the prostate during HDR brachytherapy. The median Dice coefficient between AI and reference contours was 0.92 (IQR: 0.90 – 0.94). The current study aims to assess whether the same deep learning AI algorithm can improve the quality of prostate contours for new learners (resident or fellow/new attending)

performing prostate HDR brachytherapy.

2. OBJECTIVES

2.1 Study Design

This is a Phase II prospective study evaluating a deep learning AI algorithm for auto-contouring of the prostate during HDR prostate brachytherapy with the needles in place by new learners. The study will be conducted with a randomized design. Each patient will be assigned to a new learner and then randomized to manual versus AI-assisted contouring. The randomization will be stratified by new learner type: resident versus fellow/new attending. The hypothesis is that AI-assisted learner contours will have improved Dice coefficients with respect to clinically approved contours compared with manual learner contours. All brachytherapy contours will undergo review by the treating radiation oncologist who is the experienced clinician for clinical approval prior to patient treatment. The experienced clinician will be blinded to the randomization. Clinicians will not be registered in OnCore.

DF/HCC Office of Data Quality will perform randomization. If the new learner of a case is a resident, then the "resident" randomization tab will be used for the randomization. If the new learner of a case is a fellow/new attending, then the "fellow/new attending" tab should be used to determine which arm the case goes to.

2.2 Primary Objective

The primary objective of the study is to evaluate the Dice coefficient [0: no match, 1: complete match] between the final clinically approved brachytherapy prostate contours versus the manual and AI-assisted contours provided by the new learner.

2.3 Secondary Objectives

- To measure contouring time-to-complete needed to generate and edit manual vs AI-assisted contours for a new learner.
- To evaluate the subjective impressions of AI or manual contours by the new learner based on survey responses.
- To evaluate the subjective impressions of AI or manual contours by the experienced clinician based on survey responses.
- To calculate Dice coefficients of expert clinician contours between TRUS images with implanted needles and TRUS images after removal of bottom needle rows.

3. PARTICIPANT SELECTION

3.1 Eligibility Criteria

1. 18 years of age and older
2. Deemed suitable candidates for whole gland HDR prostate brachytherapy under general anesthesia as a monotherapy, boost or salvage treatment.

3.2 Exclusion Criteria

1. Prior permanent seed LDR brachytherapy implant
2. Prior transurethral resection of the prostate (TURP)
3. Presence or insertion of a rectal spacer
4. Focal HDR brachytherapy treatment ie. not whole prostate

3.3 Inclusion of Women and Minorities

All patients with a prostate of all races and ethnic groups are eligible for this trial.

4. PRETREATMENT EVALUATIONS/MANAGEMENT

- Within 90 days prior to registration
 - Informed consent
 - Diagnosis and staging information
 - Oncologic history

5. REGISTRATION PROCEDURES

5.1 General Guidelines for DF/HCC Institutions

Institutions will register eligible participants in the Clinical Trials Management System (CTMS) OnCore. Registrations must occur prior to the initiation of any protocol-specific therapy or intervention. Any participant not registered to the protocol before protocol-specific therapy or intervention begins will be considered ineligible and registration will be denied.

An investigator will confirm eligibility criteria and a member of the study team will complete the protocol-specific eligibility checklist.

The eligibility checklist(s) and all pages of the consent form(s) will be emailed to ODQ at [contact]. The ODQ will (a) review the eligibility checklist, (b) register the participant on the protocol, and (c) randomize the participant.

Randomization can only occur during ODQ business hours (8:30am - 5pm Eastern Time, Monday through Friday excluding holidays).

An email confirmation of the registration and/or randomization will be sent to the study coordinator(s) from the registering site, treating investigator and registering person immediately following the registration and/or randomization.

Following registration, participants may begin protocol-specific therapy and/or intervention. Issues that would cause treatment delays should be discussed with the Principal Investigator (PI) of the registering site. If the subject does not receive protocol therapy following registration, the subject must be taken off study in the CTMS (OnCore) with an appropriate date and reason entered.

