6.5 Contour Evaluation, Treatment Planning, and Treatment Delivery

The experienced clinician will review and edit all contours for final approval and clinical use for HDR prostate radiotherapy planning and treatment. Treatment planning will be done in the usual fashion by the brachytherapy medical physicist using Oncentra prostate treatment planning software. The experienced clinician will review and approve the HDR brachytherapy treatment plan per institutional metrics and constraints. The HDR brachytherapy plan will be delivered to the prostate using an iridium-192 afterloader per standard operating procedure.

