9. STATISTICAL CONSIDERATIONS

9.1 Study Design/Endpoints

The primary objective of this study is to evaluate whether AI-assisted contours perform better than manual contours as measured by the Dice coefficient between the final contours used for treatment delivery versus the contours, either manual or AI-assisted, provided by the new learners. Patients will be accrued in one stage. Each patient will be assigned to a new learner and then randomized to manual versus AI-assisted contouring. The randomization will be stratified by new learner type: resident versus fellow/new attending.

The experienced clinician will be blinded to the randomization of the contouring method by the

new learner. The prostate contour generated by the new learner will then undergo review by the experienced clinician. The dice coefficient between the new learner prostate contour and the experienced clinician contour will be calculated. The experienced clinician will approve the prostate brachytherapy contours to be used clinically for HDR prostate radiotherapy planning and treatment.

[figure not shown]

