9.7 Analysis of Secondary Endpoints

- Descriptive statistics will be used to characterize measurement of contouring time-to-complete needed to generate and edit manual vs AI-assisted contours for a new learner. The contouring time will be compared between the two groups using the t-test.
- Likert scale data from the new learner and experienced clinician surveys will be reported using mean and standard deviation and compared between the two arms using a t-test¹⁰.
- The percentage of correct predictions by the experienced clinician of whether the prostate was contoured with or without AI-assistance will be reported along with 90% exact binomial confidence interval.
- The prostate contour quality score of the new learner's prostate contour presented to the experienced clinician during radiotherapy plan development with and without AI-assistance, described using descriptive statistics and compared using the chi-squared test.

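### Section 5.1 emails the randomization result to the treating investigator, who on the natural reading is the clinician meant to be blinded and whose edits define the primary endpoint

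*Protocol*

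**What the plan says.** Protocol section 2.1 identifies the assessor: "All brachytherapy contours will undergo review by the treating radiation oncologist who is the experienced clinician for clinical approval prior to patient treatment". It then sets the blind: "The experienced clinician will be blinded to the randomization". Section 9.1 repeats the blinding with respect to the contouring method.

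Section 5.1 has the Office of Data Quality (ODQ) check eligibility, register the participant and randomize. It continues that an "email confirmation of the registration and/or randomization will be sent to the study coordinator(s) from the registering site, treating investigator and registering person", and this happens "immediately following the registration and/or randomization". The same section requires registration before any protocol-specific intervention.

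Section 6.5 gives the blinded clinician's task: "The experienced clinician will review and edit all contours for final approval and clinical use for HDR prostate radiotherapy planning and treatment". Sections 2.2, 9.1 and 9.6 define the primary endpoint as the Dice coefficient between the learner's contour and that final approved contour. Section 9.7 adds a secondary endpoint that presupposes the blind: "The percentage of correct predictions by the experienced clinician of whether the prostate was contoured with or without AI-assistance will be reported", with a 90% exact binomial confidence interval.

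**The concern.** The protocol relies on blinding one person and then lists the treating investigator among those who are told the randomization result. In section 2.1 the treating physician and the blinded clinician are the same person.

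The blind matters more here than in a trial with an independent reference standard. The reference contour is made by editing the contour under test. If the clinician edits lightly, Dice rises towards 1; if heavily, it falls. A clinician who knows that AI was used may trust the contour and change little, or distrust it and change more. Either way the arm difference then reflects the clinician's attitude as well as contour quality.

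Three secondary results in section 9.7 are exposed as well: the clinician survey, the contour quality score, and the percentage of correct guesses. The last cannot be interpreted if the clinician had already been sent the answer.

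**Working it through.** **Consistency check**

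| Question | Protocol | Answer |
|---|---|---|
| Who is the experienced clinician? | 2.1 | The treating radiation oncologist |
| May that person know the arm? | 2.1, 9.1 | No |
| Who is sent confirmation of randomization? | 5.1 | Study coordinator(s), treating investigator, registering person |
| When? | 5.1 | At once, and so before the procedure |
| Whose contour is the primary reference? | 6.5, 9.1, 9.6 | The experienced clinician's |
| Does any readable text withhold the arm from that email? | – | No |

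The new learner, who must know the arm in order to carry it out, is not on the 5.1 list, whereas the treating investigator is. This suggests generic registration text that was not adapted to this design.

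**Plan figures used for the illustration (section 9.3)**

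Inputs: difference 0.92 − 0.87 = 0.05, SD 0.05, one-sided alpha 0.10, power 0.90, intra-cluster correlation (ICC) 0.15, 3 patients per learner per arm.

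- Total n by normal approximation = 4 × (SD/difference)² × (1.2816 + 1.2816)² = 4 × 1 × 6.57 = 26.3. Noncentral-t power is 0.898 at 13 + 14 = 27, so the plan's 27 is reproduced.
- Design effect = 1 + (3 − 1) × 0.15 = 1.30, and 27 × 1.30 = 35.1, which the plan takes to 36. Effective n = 36/1.30 = 27.7, with power 0.904.

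The sample size is not in dispute; these inputs only set the scale.

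**Illustrative effect of an arm-related editing shift**

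The shift is an assumption, because the documents give no value for it. With no true difference and 18 patients per arm, the noncentrality is

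ncp = shift / (0.05 × √f) × √(36/4) = 3 × shift / (0.05 × √f),

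and the false-positive rate is P(T > t at the 90th percentile) under the noncentral t. Two variance factors f bracket the result:

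- f = 1.30, the plan's inflation (df = 27.7 − 2 = 25.7).
- f = 1 − 0.15 = 0.85, which applies if learners contour in both arms, so that learner variation cancels from the comparison (df 29 assumed).

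| Assumed shift favouring AI | f = 1.30: ncp, false-positive rate | f = 0.85: ncp, false-positive rate |
|---|---|---|
| 0 | 0, 0.10 | 0, 0.10 |
| 0.01 | 0.53, 0.22 | 0.65, 0.26 |
| 0.02 | 1.05, 0.40 | 1.30, 0.50 |

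A bias of 0.01/0.05 = one fifth of the planned effect therefore more than doubles the nominal error rate. If the bias runs against AI, the loss is in power: with f = 1.30 and a true difference of 0.05, the apparent difference falls to 0.04 or 0.03, ncp falls from 2.63 to 2.10 or 1.58, and power falls from 0.90 to 0.79 or 0.61.

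**The case against.** The contradiction depends on two readings that no sentence spells out. Section 5.1 says treating investigator and section 2.1 says treating radiation oncologist, and the protocol never equates the terms. Section 5.1 also does not say that the email shows the arm; a notice that registration or randomization had taken place would satisfy its wording. The registration policy cited in section 5.2 and the workflow figures cannot be seen and might settle who receives the arm. The specific blinding rule could be taken to override a general registration paragraph. Finally, the shifts of 0.01 and 0.02 are not from the documents, and the clinician's responsibility for the treated contour limits discretionary editing.

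Part of this stands. The size of any bias is unknown and its direction is open, so the figures above are illustrative and the finding does not rest on them. The guess endpoint is lost only if the email carried the arm and was read.

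The rest is weak. Section 2.1 makes the patient's treating physician the experienced clinician, other sites are marked not applicable, and nothing separates the two roles. A confirmation of randomization ordinarily states the assignment. A blind that protects the primary endpoint should not depend on an unwritten restriction or on staff choosing which section prevails. Nor is this a detail left to a statistical analysis plan: the protocol itself names the recipients, and the list conflicts with its own blinding rule.

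**Conclusion.** The concern holds. Section 5.1, followed as written, conflicts with the blinding in sections 2.1 and 9.1, and the person affected produces the reference for the primary endpoint. The conclusion assumes that the treating investigator is the treating radiation oncologist and that the confirmation shows the arm; both are the natural reading, and no readable text says otherwise.

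The amount of bias cannot be derived from the documents. Under the assumed shifts of 0.01 and 0.02 Dice towards AI, the false-positive rate would be about 22–26% and 40–50% instead of 10%. Analysis by intention to treat (section 9.8.2) and the random effect for learner (section 9.6) do not remove bias in the reference contour, and it cannot be repaired once the contours have been edited. This must be fixed before accrual.

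**What to change.** Amend section 5.1 so that the arm is sent only to the study coordinator and the assigned new learner. The treating investigator, as experienced clinician, should receive a registration confirmation that omits it. Because the registering person is on the same list, add that whoever acts as experienced clinician for a case may not be its registering person or have access to its arm field. This second safeguard goes slightly beyond the quoted conflict but closes the same route.

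The cost is a short text edit in 5.1 and a changed email distribution list. It needs no added patients or staff and does not alter the clinician's responsibility for approving the treated contour.

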5.2 Registration Process for DF/HCC Institutions

Applicable DF/HCC Policy REGIST-101 must be followed.

5.3 General Guidelines for Other Investigative Sites

N/A

5.4 Registration Process for Other Investigative Sites

[figure not shown]
N/A

6. TREATMENT PLAN

6.1 Study contouring workflow

As mentioned above, the goal of this study is to evaluate whether artificial-intelligence can improve the quality of implanted prostate contours for new learners by comparing the dice coefficient of manual versus AI-assisted learner prostate contours to the final clinically approved prostate contours. The diagram below describes the workflow for the study.

6.2 New learner credentialing

All new learners will undergo a credentialing process prior to participation on the study. New learners must be a radiation oncology resident, fellow, or a new attending who has performed less than 20 ultrasound-based prostate HDR brachytherapy cases independently.

The credentialing procedure will take place over a 60 minute period under the direction of the principal investigator. First, the principal investigator will review a power-point presentation showing relevant anatomy of the prostate on ultrasound images with needles in-place. The principal investigator will then ask the new learner to provide contours of the prostate for 3 cases (case 1, case 2, and case 3). For each case, the principal investigator will then show the actual clinical contours utilized for treatment planning, and point out discrepancies between the new learner and clinical contours.

6.3 Dose/Fractionation

High dose rate brachytherapy will be delivered to the clinical target volumes with prescription doses at the experienced clinician discretion based on the clinical scenario. Participation in the trial does not alter the standard of care treatment.

6.4 Target and Organs-at-risk (OAR) Volumes

All contouring of prostate will be done on TRUS images which is the usual HDR brachytherapy workflow.

- Prostate_Learner_Image1 = prostate contour prior to needle insertion on TRUS images #1
- Prostate_Learner_Image2 = prostate contour generated by the new learner with or without AI assistance on TRUS images #2 with needles
- Prostate_Clinician_Image2 = prostate contour reviewed and edited by experienced clinician
- CTV = clinical target volumes contoured by experienced clinician (prostate +/- seminal vesicle target)
- Prostate_Clinician_Image3 = prostate contoured by experienced clinician on TRUS images #3 following HDR treatment delivery with the bottom half needle rows removed to better visualize the anterior border of the prostate

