6.6 Post-treatment TRUS

Following treatment plan delivery, the bottom half of the interstitial prostate needles will be removed. TRUS images #3 will be obtained with better visualization of the anterior border of the prostate. These TRUS images represent the “ground truth” in terms of the location and outline of the prostate.

The interstitial implant will then be completely removed, and the patient will be transferred to recovery area.

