9.2 Primary Objective

The primary objective of this study is to evaluate whether the addition of artificial intelligence can improve the quality of implanted prostate contours as measured by the Dice coefficient between the final contours used for treatment delivery versus the contours, either manual or AI-assisted, provided by the new learners. The Dice coefficient ranges between 0 and 1, where 0 indicates no match, and 1 indicates complete match.

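### The primary Dice scores each learner contour against the clinician's edited version of that same contour, so it measures how much was edited, and the image #3 reference is never compared by arm

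*Protocol*

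**What the plan says.** Three contours matter here, all defined in Protocol 6.4. The learner draws Prostate_Learner_Image2 on the TRUS images with needles in place, with or without AI. The clinician's contour on the same images is described as "Prostate_Clinician_Image2 = prostate contour reviewed and edited by experienced clinician". The third, Prostate_Clinician_Image3, is drawn by the clinician after treatment, once the bottom half of the needle rows is out.

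The sequence is explicit. Section 9.1: "The prostate contour generated by the new learner will then undergo review by the experienced clinician". Section 6.5: "The experienced clinician will review and edit all contours for final approval and clinical use for HDR prostate radiotherapy planning and treatment".

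The primary endpoint (2.2, 9.1, 9.6) is the Dice between the learner's contour and the approved contour. Section 9.2 frames the question as whether AI "can improve the quality of implanted prostate contours as measured by the Dice coefficient between the final contours used for treatment delivery" and the learner's contour.

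Of the post-treatment images, section 6.6 says: "These TRUS images represent the “ground truth” in terms of the location and outline of the prostate". Their one stated use is the last secondary objective in 2.3: "To calculate Dice coefficients of expert clinician contours between TRUS images with implanted needles and TRUS images after removal of bottom needle rows". No learner contour enters that comparison, no comparison between arms is named, and 9.7 lists no analysis for it.

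On masking, section 2.1 states: "The experienced clinician will be blinded to the randomization".

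**The concern.** A reference made by editing the object under test is not an independent standard. The Dice between a contour and its edited version reflects how much the editor changed. That amount depends on how wrong the contour was and on how much of the error the editor noticed and chose to correct. Only the first of these is contour quality.

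Masking the arm limits deliberate favouring. It does not stop the clinician from anchoring on the outline displayed, and it does not ensure that AI-assisted and manual outlines are accepted equally readily. Section 1.2 itself says that delineation on TRUS with needles in place is difficult, so the approved image #2 contour cannot be assumed correct.

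At stake is the meaning of a positive result. A difference in the primary Dice shows closer agreement with the approved contour. On its own it cannot separate a more accurate contour from one that was edited less. The planned difference is only 0.05, so a modest difference in editing between arms would matter.

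**Working it through.** **Step 1: the plan's own figures.** Section 9.3 gives means 0.87 and 0.92, SD 0.05, one-sided alpha 0.1, power 0.9, ICC 0.15, 3 patients per learner per arm, and N = 27 inflated to 36. The allocation ratio is not stated; I take 1:1.

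- Before inflation, noncentral t power is 0.898 at 13 + 14 = 27 and 0.907 at 14 + 14 = 28.
- Design effect: 1 + (3 − 1) × 0.15 = 1.30, and 27 × 1.30 = 35.1, taken as 36.
- With 18 per arm: SE = 0.05 × √(1.30 × 2/18) = 0.0190; 0.05/0.0190 = 2.63; power on 34 df = 0.906.

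The sample size reproduces and is not in dispute.

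**Step 2: a simple model of editing.** Suppose the clinician corrects a share f of the learner's true discrepancy. Then, approximately, observed (1 − Dice) = f × true (1 − Dice). At f = 0 the observed Dice is 1.0 whatever the accuracy. The shares below are assumptions; the protocol gives no data on them.

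**Step 3: equal true quality, Dice 0.90 in both arms.** The false difference is 0.10 × (f manual − f AI). The test is one-sided at 0.10 with 34 df and critical value 1.307. Two variance factors are used: 1.30 (the plan's) and 0.85 = 1 − ICC (the same learners contributing to both arms, so the learner effect cancels). The SD is either held at 0.05 or multiplied by f in each arm.

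| f manual / f AI | False difference | P(AI declared better), SD fixed: 1.30 / 0.85 | SD scaled: 1.30 / 0.85 |
|---|---|---|---|
| 0.8 / 0.8 | 0 | 0.10 / 0.10 | 0.10 / 0.10 |
| 0.8 / 0.7 | 0.01 | 0.22 / 0.26 | 0.28 / 0.34 |
| 0.8 / 0.6 | 0.02 | 0.40 / 0.50 | 0.57 / 0.70 |
| 0.6 / 0.8 | −0.02 | at most 0.01 | at most 0.01 |

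For the 0.8 / 0.6 row on the plan's variance:

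- SD fixed: 0.02/0.0190 = 1.05, giving 0.40.
- SD scaled: the SDs are 0.04 and 0.03, SE = √(1.30 × (0.0016 + 0.0009)/18) = 0.0134, and 0.02/0.0134 = 1.49, giving 0.57.

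**Step 4: a true gain with the shares reversed.** Take true Dice 0.87 and 0.92, with f = 0.6 manual and 0.8 AI. The observed difference is 0.13 × 0.6 − 0.08 × 0.8 = 0.078 − 0.064 = 0.014 instead of 0.05. Power on the plan's variance is 0.29 (SD fixed) or 0.40 (SD scaled).

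**Step 5: equal anchoring.** With f = 0.6 in both arms and the SD scaled, the effect and its SE shrink together and power stays at 0.906. I claim no loss of power for this case.

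**Step 6: what an image #3 comparison could deliver.** The 90% half-width is t(0.95, 34) × SD × √(1.30 × 2/18), with t = 1.69.

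- No added noise, SD 0.05: SE 0.0190, half-width 0.032.
- Assumed added SD 0.03: √(0.05² + 0.03²) = 0.058, SE 0.0222, half-width about 0.037.
- Assumed added SD 0.05: √(0.05² + 0.05²) = 0.071, SE 0.0269, half-width 0.045.

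**The case against.** The comparator is stated openly throughout, and 9.2 can be read as defining quality operationally. How much a blinded expert changes a learner's contour before clinical use is a meaningful outcome for a teaching tool. This stands, and it is why the endpoint can remain primary. It does not justify reading the result as accuracy without a check.

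The protocol also has safeguards. The clinician is masked, and 9.7 reports how often the clinician correctly guesses AI use. Section 9.7 also compares by arm a quality score for the "prostate contour presented to the experienced clinician during radiotherapy plan development with and without AI-assistance". The guess rate bears on recognition of the arm, not on anchoring to the outline shown. The quality score is a partial check, but it is subjective and concerns the same contour seen by the same clinician.

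Section 2.3 does not forbid other uses of image #3, and a statistical analysis plan might add some. But 2.3 itself names which contours are compared, and the learner's is not among them. The planned comparison does test the approved contour against image #3, yet it says nothing directly about the learner's contour.

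The editing shares have no basis in the documents, and the result moves with the variance assumed. That is correct: the figures show sensitivity, not an expected bias.

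Finally, image #3 is imperfect and its interval would be wider than the 0.02 bias illustrated. That also stands, and it limits the remedy to a supportive estimate.

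**Conclusion.** The concern holds. The primary Dice is taken against an edited version of the contour being scored, while 9.2 and 9.6 present it as contour quality. The contour on the images that the protocol calls the ground truth has no stated comparison by arm and none with the learner's contour.

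The bias is a risk, not a demonstrated fact. It needs the share of error corrected to differ between arms, and it could run either way. On assumed shares of 0.8 and 0.6, it would raise the false-positive chance from 0.10 to between 0.40 and 0.70. With the shares reversed, it would reduce a true gain of 0.05 to an apparent 0.014. With equal shares there is no false difference. The sample size and the primary test are unaffected. The change should be made because it is cheap and bears on the trial's stated question.

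**What to change.** 1. Add to 9.7 a named secondary comparison by arm of Dice(Prostate_Learner_Image2, Prostate_Clinician_Image3), using the same mixed model as the primary analysis.
2. Report Dice(Prostate_Clinician_Image2, Prostate_Clinician_Image3) by arm, to show whether the approved contours agree with image #3 equally well in both arms.
3. Describe the primary result as agreement with the approved, edited contour. Interpret any claim of improved quality alongside the image #3 estimate and its confidence interval, not by a pass/fail rule on its direction.

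The cost is analysis work only: all the contours are already collected, and 2.3 already plans a Dice across the two image sets. Named before results are seen, the comparison is prespecified; added later, it would be post hoc.

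The downsides should be stated. Registration between images #2 and #3 and shift of the gland add noise. The same clinician draws both contours, and the protocol text does not say that image #3 is contoured without sight of the approved image #2 contour, so carry-over is possible. With a 90% half-width of about 0.032 to 0.045, the comparison should stay secondary and be read as an estimate.
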